#### 4.1.2 Hematologic Support

- Due to the hematologic abnormalities associated with MDS, management of hematologic toxicity in MDS participants will be at the discretion of the PI/treating investigator.
- Transfusions of red blood cells and platelets will be allowed per the appropriate participant-specific hematologic parameters.
- G-CSF may be administered for participants with ANC < 500/mcL per the discretion of the treating physician.
- Thrombopoietin agonists may be administered for participants with PLT < 50 x 10^9/L per the discretion of the treating physician.

- Participants receiving a stable dose of erythropoiesis-stimulating agent (ESA) for at least 1 month at the time of study entry may continue to receive ESA, but changes in dosing of ESA or new start of ESA within <30 days are not permitted.

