## 2.1.2 Exclusion Criteria

2.1.2.1 Participants with platelet transfusion-refractory thrombocytopenia, with inability to keep platelet threshold above 10K/mcL with transfusions or those with ongoing or uncontrolled hemorrhagic complications.

2.1.2.2 Participants with clinically significant neutropenia, defined as ANC <100 cells/mcL with frequent hospitalizations for infection (average > 1 hospitalization per month in the past 6 months).

2.1.2.3 Participants on treatment with a myeloid growth factor (e.g., G-CSF) within 14 days prior to initiation of study treatment.

2.1.2.4 History of allergic reactions attributed to compounds of similar chemical or biologic composition to HMAs or other agents used in study.

2.1.2.5 Uncontrolled intercurrent illness evaluated by history, physical exam, and chemistries or situations that would limit compliance with study requirements, interpretation of results or that could increase risk to the participant

2.1.2.6 Participants with the following cardiac conditions: symptomatic congestive heart failure, unstable angina pectoris, or uncontrolled cardiac arrhythmia as assessed by electrocardiogram (ECG).

- 2.1.2.7 Pregnancy (confirmed with  $\beta$ -HCG serum or urine pregnancy test performed in individuals of childbearing potential at screening)
- 2.1.2.8 Presence of any other malignancy (except basal and squamous cell carcinoma of the skin, or stable chronic cancers on hormone or targeted therapy) for which participant received systemic anticancer treatment (except maintenance therapy) within 24 months prior to treatment.
- 2.1.2.9 Participants with active/uncontrolled Hepatitis B
- 2.1.2.10 Participants with active/uncontrolled Hepatitis C
- 2.1.2.11 Participants with active/uncontrolled HIV infection or AIDS.
- 2.1.2.12 Participants currently taking contraindicated medications for HIV, Hepatitis B, or Hepatitis C disease control ([Appendix L](#))

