### 3.3.2.2.1 Hematologic toxicities

Toxicity	Recommended Action*
Thrombocytopenia	
Grade 2 (PLT $\leq$ 75,000/mcL)	
 
Maintain dose of KPT-8602 and Inqovi.
 
Consider dose reduction of any anti-platelet agents.
 
Start PPI.
 

Grade 3 or 4 thrombocytopenia (PLT $\leq$ 50,000/mcL) without bleeding	
 
In cases where there is still significant disease involvement in the bone marrow:             
 
The treating physician, in consultation with the PI, may continue KPT-8602 and Inqovi at the same dose level
 
 
 
Otherwise, the following guidelines should be followed:             
 
Hold KPT-8602 and Inqovi until improves to <math>\leq</math> Grade 2 or baseline.                     
 
If improves to <math>\leq</math> Grade 2 or baseline within 72 hours:                             
 
Resume KPT-8602 and Inqovi at the same dose
 
 
 
If does not improve to <math>\leq</math> Grade 2 or baseline within 72 hours:                             
 
Hold KPT-8602 and Inqovi for the remainder of the current cycle.
 
Reduce KPT-8602 by one dose level with the next cycle
 
Resume Inqovi at the same dose for the next cycle (first occurrence) or reduce Inqovi by one dose level for the next cycle (second or later occurrences)
 
Note: Toxicity must resolve to <math>\leq</math> Grade 2 or baseline before drugs can be resumed
 
 
 
 
 
In addition, the following steps should be taken for all cases:                     
 
Consider initiating a platelet growth factor per institutional guidelines.
 
Monitor platelet counts at least twice weekly and closely monitor for any bleeding signs/symptoms.
 
Transfuse as per institutional guidelines.
 
Consider dose reduction of any anti-platelet agents.
 
Start PPI.
 
 
 
 
 

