	
 
▪ If improves to <math>\leq</math> Grade 3 or baseline within 72 hours:                     
 
• Resume KPT-8602 and Inqovi at the same dose.
 
 
 
▪ If does not improve to <math>\leq</math> Grade 3 or baseline within 72 hours:                     
 
• Hold KPT-8602 and Inqovi for the remainder of the current cycle.
 
• Reduce KPT-8602 by one dose level with the next cycle.
 
• Resume Inqovi at the same dose for the next cycle (first occurrence) or reduce Inqovi by one dose level for the next cycle (second or later occurrences).
 
• Note: Toxicity must resolve to <math>\leq</math> Grade 3 or baseline before drugs can be resumed
 
 
 
• Consider use of growth factors.
 
• If growth factors are implemented, for participants who achieve neutrophil levels <math>>1000/\text{mcL}</math> for <math>>4</math> weeks, KPT-8602 may be re-escalated with the next cycle of therapy, with frequent monitoring implemented.
 

Grade 3 or 4 neutropenia with fever	
 
• Implement broad-spectrum anti-microbial agents per institutional guidelines.
 
• Consider use of growth factors.
 
• Hold KPT-8602 and Inqovi for the remainder of the cycle and until fever resolves and the participant is clinically stable, then:                     
 
○ Reduce KPT-8602 by one dose level with the next cycle.
 
○ Resume Inqovi at the same dose for the next cycle (first occurrence) or reduce Inqovi by one dose level with the next cycle (second or later occurrences).
 
 
 
• If growth factors are implemented, for participants who achieve neutrophil levels <math>>1000/\text{mcL}</math> for <math>>4</math> weeks, KPT-8602 may be re-escalated with the next cycle of therapy, with frequent monitoring.
 

\*Once the lowest dose level has been reached, if toxicity persists, discontinue drug.

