Neutrophil response (HL-N)	Pre-treatment ANC $<1.0 \times 10^9/L$	

• At least 100% increase and an absolute increase <math>>0.5 \times 10^9/L</math>

• Increments of neutrophils also for participants with a pre-treatment ANC of <math>\geq 1.0 \times 10^9/L</math> are to be reported

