## 10 STATISTICAL CONSIDERATIONS

### 10.1 OBJECTIVES AND ENDPOINTS

OBJECTIVES	ENDPOINTS	JUSTIFICATION FOR ENDPOINTS
Primary		
Phase I: To determine the recommended phase 2 dose (RP2D) of KPT-8602 in combination with Inqovi in adult participants with higher-MDS	- Recommended phase 2 dose (RP2D), as determined by the number of participants with DLTs reported at each dose level studied (Section 3.1.1 ) -Any toxicities identified from Day 1 of study drug through 28 days after the first dose. AEs are reported by type and grade. -ORR (defined as CR+PR+mCR with HI) per each cohort Responses will be assessed after every cycle with CBC and at the end of Cycles 2 and 6 with bone marrow assessment during treatment and every 3-6 months after that until time of disease relapse, disease progression, or death, or 8 years, whichever occurs first.	Standard endpoint for Phase I protocol Efficacy evaluation, standard for Phase II protocol
Secondary		
Phase I: To characterize the PK properties of KPT-8602 in combination with Inqovi in MDS participants	-AUC, half-life, and steady state concentration, measured by the KPT-8602 blood concentration 1, 2, 3, 4, 8, 24 and 48 hours after the product administration on days 8 and 21 of cycle one	PK studies to evaluate for adequate absorption of therapy and further define half-life/AUC and other properties of the study drug, when given in combination with Inqovi
Phase II: To further evaluate the PK properties and safety of KPT-8602 in combination with Inqovi in MDS participants	-Safety, as measured by: Incidence of AEs, SAEs; and AEs leading to discontinuation, death, and laboratory abnormalities, assessed at least weekly through cycle 3 and then at the start and every cycle after that	Confirm safety of the study drug at the RP2D
Exploratory		
To evaluate the relationship between KPT-8602 exposure (PK) and response	Each of these will be evaluated using descriptive methods and reported as exploratory results. If any statistical	Evaluate mechanism of the study drug, target engagement,

OBJECTIVES	ENDPOINTS	JUSTIFICATION FOR ENDPOINTS

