## 10.2 STATISTICAL HYPOTHESIS AND SAMPLE SIZE DETERMINATION

The trial will begin with a phase I dose-escalation phase using a standard 3+3 design which will enroll participants with relapsed/refractory HR-MDS. Up to 18 participants may be enrolled based on the 3+3 design.

Participants will be eligible for the DLT evaluation if  $\geq 90\%$  (9 out of 10 doses) of KPT-8602 and  $\geq 80\%$  (4 out of 5 doses) of Inqovi were taken within the DLT period. Participants not evaluable for toxicity, will be replaced in the dose level.

Phase II will use a Simon's minimal two-stage design, applied separately as noted below:

- Trial will be conducted using a Simon minimax two-stage phase II trial design to rule out an unacceptably low response rate of 25% ( $p_0=0.25$ ) in favor of an improved response rate of 45% ( $p_1=0.45$ ) in order to determine if the combination of KPT-8602 with Inqovi will be able to improve upon an expected 30-40% response rate in participants who have received other agents. With two-sided alpha=0.05 and beta=0.20, the first stage will enroll 21 evaluable participants, and if 0 to 5 of the 21 have a response, then no further participants will be accrued. If 6 or more of the first 21 participants have a response, then accrual would continue until a total of 43 evaluable participants have been treated. If there are only 6-16 participants with a response out of 43 participants, this would be an uninterestingly low response rate. If there were 17 or more of 43 (39.5%) who experienced a response, treatment would be sufficiently interesting to warrant further study in later trials. The probability of early termination under the null (25%) response rate is 56.7%.

It is expected that up to 12-15 participants with MDS may be accrued per year. Thus, in order to accrue up to  $18 + 43 = 61$  participants (which may be reduced by up to 6 if up to 6 participants in phase I may be included in phase II), and to allow for a small number of inevaluable participants (12), it is expected that 3-4 years may be required to accrue the required 73 participants. Note: To allow for screen failures (7), the accrual ceiling will be set at 80 participants for the purposes of the NIH accrual ceiling.

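### Response criteria score neutrophil and platelet counts without regard to G-CSF, thrombopoietin agonists or platelet transfusion, so support can turn a marrow response into a primary-endpoint responder

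*Combined protocol and SAP*

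**What the plan says.** **Endpoint.** Section 10.1 gives the primary efficacy endpoint as "ORR (defined as CR+PR+mCR with HI) per each cohort". HI alone is not a response, and marrow CR without HI is not counted.

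**Support on study.** Section 4.1.2 says "G-CSF may be administered for participants with ANC < 500/mcL per the discretion of the treating physician". It also allows thrombopoietin agonists at platelets below 50 x 10^9/L, and red cell and platelet transfusion. The toxicity tables in 3.3.2.2.1 prompt support again: "Consider initiating a platelet growth factor per institutional guidelines" for Grade 3-4 thrombocytopenia, and consideration of growth factors for neutropenia.

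**Scoring.** In 6.3.1, HI-N applies to a pre-treatment ANC below 1.0 x 10^9/L and requires "At least 100% increase and an absolute increase" above 0.5 x 10^9/L. HI-P is a platelet increase. The blood component of CR requires neutrophils of at least 1.0 and platelets of at least 100 x 10^9/L, and PR carries over the CR criteria apart from the marrow items. None of these rows says that counts must be free of G-CSF, thrombopoietin agonist or platelet transfusion. Only the HI-E rows take transfusion into account. Appendix D repeats the same rules.

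**Baseline.** Exclusion 2.1.2.3 removes "Participants on treatment with a myeloid growth factor (e.g., G-CSF) within 14 days prior to initiation of study treatment".

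**The concern.** For marrow CR, HI decides whether the participant counts, and a permitted co-treatment can supply the count rise that HI-N or HI-P asks for. For neutrophils the comparison is uneven by design: the baseline is off G-CSF and the later counts need not be.

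Phase II is a single-arm test against a fixed rate, with no control arm in which the same effect would cancel. Both decisions rest on small integers: 5 versus 6 responders of 21 at stage 1, and 16 versus 17 of 43 at the end. If the rule is left open, it will have to be settled after an open-label team knows who received G-CSF.

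**Working it through.** **1. The plan's own design.** Section 10.2 sets out "to rule out an unacceptably low response rate of 25" per cent "in favor of an improved response rate of 45" per cent, with two-sided alpha 0.05 and beta 0.20. The trial stops at 5 or fewer of 21 and succeeds at 17 or more of 43.

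- Early stopping: PET(p) = P(X1 <= 5), X1 ~ Bin(21, p).
- Success: S(p) = sum over x = 6 to 21 of P(X1 = x) x P(X2 >= 17 - x), X2 ~ Bin(22, p).

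Results: PET(0.25) = 0.5666 (the plan states 56.7%), S(0.25) = 0.0245, S(0.45) = 0.8005. A minimax search at an upper-tail alpha of 0.025 returns the same design. The plan's figures reproduce.

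**2. Can the written rule score a supported count?** Take an invented participant with marrow CR, baseline ANC 0.4 x 10^9/L, and ANC 1.1 on G-CSF.

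- Absolute rise: 1.1 - 0.4 = 0.7, above 0.5.
- Relative rise: 0.7 / 0.4 = 175%, above 100%.
- ANC 1.1 also passes the CR neutrophil threshold of 1.0.

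If held for the 4 weeks that heads the response table, this is HI-N as written. Marrow CR becomes marrow CR with HI and counts in the ORR. Remove the marrow response and nothing counts, because CR, PR and marrow CR all include a marrow criterion.

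**3. Effect on the decision.** Hold the true ORR at 25% and add d percentage points of support-driven responses. The documents give no value for d, so this is an assumed range.

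| d (points) | Expected extra responders in 43 | Scored ORR | PET | S = P(declare success) |
|---|---|---|---|---|
| 0 | 0 | 25% | 0.567 | 0.0245 |
| 2 | 0.02 x 43 = 0.86 | 27% | 0.482 | 0.049 |
| 3 | 0.03 x 43 = 1.29 | 28% | 0.441 | 0.066 |
| 5 | 0.05 x 43 = 2.15 | 30% | 0.363 | 0.114 |

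About one extra scored responder in 43 doubles the false-positive probability, and the stage 1 stop weakens with it.

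**4. Effect of a stricter rule on power.** If a support-free rule also misses true responders, and this takes 3 or 5 points off a true 45% (assumed), then S(0.42) = 0.67 and S(0.40) = 0.57, against 0.80 as designed.

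**The case against.** **The routes are narrow.** This stands. Every ORR component needs a marrow response. CR also needs Hgb of at least 11 g/dL, platelets of at least 100 x 10^9/L, no blood blasts and normal maturation, so G-CSF supplies one item of several. The 4-week duration makes platelet transfusion a weak route, although the HI-P row states no duration of its own.

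**The bias has no single direction for platelets.** This also stands. Nothing in 2.1.2 bars thrombopoietin agonists or platelet transfusion before baseline, and 2.1.2.1 contemplates transfusion-maintained counts. A supported baseline would work against HI-P. The directional argument holds for neutrophils only.

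**The cited response criteria, or the concomitant-medication record, may already deal with it.** The cited sources are not available here, so what they say on supported counts cannot be settled. The protocol reproduces the criteria as its own rules, without such a condition. Section 3.4.2 records concomitant medications to assess confounding, but Section 10 has no rule or analysis that uses them for scoring.

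**Stronger readings that a reader might infer.**

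- *A large pool of convertible participants.* Section 1.2.3.2 gives marrow CR in 3/5 + 4/10 = 7/15 (46.7%), and one might subtract the null 25% to get about 22%. This does not measure marrow CR without HI: the section does not say how many of the seven had HI, and ORR also includes CR and PR. The denominator is itself unsettled, since 3.1.2 puts 15 patients at 20 mg. If the seven were all the marrow CRs, 7/20 = 35%, and the same subtraction gives 10%.
- *The neutropenia table as a scoring case.* The line beginning "If growth factors are implemented, for participants who achieve neutrophil levels" is a re-escalation rule for KPT-8602. It does not say that the counts were taken on continuing G-CSF, and it does not govern response.
- *Erythropoiesis-stimulating agents as an equal route.* Section 4.1.2 already restricts new starts and dose changes, though its wording on timing is unclear.

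**Conclusion.** The gap is real and sits in the definition of the primary endpoint. Read literally, 6.3.1 and Appendix D let a supported neutrophil or platelet count convert a marrow response into a counted responder, mainly through G-CSF and HI-N. They do not let support produce a response by itself, and the documents do not support a claim of large or uniformly upward bias.

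The size is unknown. With a true ORR of 25% and an assumed 2 to 5 points of support-driven responses, the chance of declaring success is 0.049 to 0.114, against 0.0245 as designed. The sample size and cut-offs are sound as stated and need no change. This should be fixed before the stage 1 assessment. Because the route is narrow and its size rests on assumption, it does not by itself invalidate the design.

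**What to change.** For endpoint scoring only, with no change to who may receive support, add to 6.3.1 and Appendix D:

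- Neutrophil counts taken within 14 days after G-CSF do not count toward CR, PR or HI-N. The interval mirrors exclusion 2.1.2.3.
- Platelet counts taken on a thrombopoietin agonist started after baseline, or within a prespecified interval after a platelet transfusion, do not count toward CR, PR or HI-P. Seven days is offered as an example; it is an assumption, and the sponsor should set the interval.
- A criterion not met for this reason may be met on later off-support counts.

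Add to Section 10 a sensitivity analysis that scores responses by counts regardless of support, reported beside the primary result.

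**Cost.** Protocol wording, a programming rule and one extra table. Concomitant medications (3.4.2) and transfusions (Appendix I) are already collected, but dates of G-CSF, agonist and platelet transfusion must be precise enough to apply the intervals. The statistical cost should be stated openly: some true responders on support may be missed, with power falling to 0.67-0.57 if 3 to 5 points are lost from a true 45%. Allowing later off-support counts limits that loss. Section 10.2 does not say how support was handled in its 30-40% comparator rate, so comparability with that figure should be described as uncertain under either rule.

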#### 4.1.3 Other Supportive Care

- In order to minimize nausea, unless contraindicated, all participants will receive a serotonin receptor subtype 3 (5-HT3) antagonist (ondansetron or equivalent) before KPT-8602 dosing. This may be tapered after 1-2 cycles of treatment, per Investigator discretion.
  - 5-HT3 receptor antagonists (ondansetron 8 mg or equivalent) should be started before study treatment dosing and continued for 3 consecutive days.

### 4.2 DRUG INTERACTIONS

The risk of drug-drug interactions with KPT-8602 is low. However, administration of eltanexor with drugs that undergo substantial GSH conjugation (e.g., acetaminophen) should be minimized. See Section [14.1.7](#).

### 4.3 CONTRAINDICATED AGENTS

- No other antineoplastic, immunomodulatory, or immunosuppressive therapies, including corticosteroids (barring adrenal insufficiency supplementation dosing), should be given concomitantly while on study treatment.

## 5 CORRELATIVE STUDIES FOR RESEARCH

Participants may submit none, all, or a portion of research specific biospecimens to stay on study. Providing *all* research biospecimens is not a criterion for study inclusion and all samples are optional with the exception of pharmacokinetic (PK) samples. Any unused biological sample or derivative that is obtained from a participant during a clinical procedure on this study may be used for research and/or stored for future research purposes.

Every effort will be made to collect all research samples, including bone marrow aspirates and peripheral blood draws, at the time of a scheduled diagnostic bone marrow aspirate or blood draw for clinical purposes as listed in the study calendar and table below.

If additional tests are done for clinical purposes, additional samples will be collected also at that time(s), if feasible, and used for research.

### 5.1 BIOSPECIMEN COLLECTION

Test/assay	Volume (approx.)	Type of sample/tube(s) ^	Collection point	Location of specimen analysis
Pharmacokinetics (PK)	4 mL	Blood, SST vacutainer tubes -Serum samples should then be	Dose levels -2 and 1: C1D8 (1)Pre-dose, (2) 1 hr ( $\pm$ 10 min) post-dose, (3) 2 hr ( $\pm$ 10 min) post-dose, (4) 3 hr ( $\pm$ 10 min) post-dose,	Clinical Pharmacology Program (CPP) ; [name] laboratory

Test/assay	Volume (approx.)	Type of sample/ tube(s) ^	Collection point	Location of specimen analysis
		transferred to micronic tubes for shipping to bioanalytical lab.	
(5) 4 hr (<math>\pm</math> 20 min) post-dose, (6) 8 hr (<math>\pm</math> 20 min) post-dose, (7) 24 hr (<math>\pm</math> 1 hr) post-dose (8) 24 hr (<math>\pm</math> 1 hr) post-dose-i.e, C1D9 pre-dose
 
C1D12 (9) Pre-dose, (10) 2 hr (<math>\pm</math> 10 min) post-dose, (11) 3 hr (<math>\pm</math> 10 min) post-dose, (12) 8 hr (<math>\pm</math> 20 min) post-dose, (13) 24 hr (<math>\pm</math> 1 hr) post-dose-i.e, C1D13 pre-dose, (14) 48 hrs (<math>\pm</math> 2hr) post-dose- i.e, C1D14 pre-dose
 
Dose levels -1 and 2:
 
C1D8 (1)Pre-dose, (2) 1 hr (<math>\pm</math> 10 min) post-dose, (3) 2 hr (<math>\pm</math> 10 min) post-dose, (4) 3 hr (<math>\pm</math> 10 min) post-dose, (5) 4 hr (<math>\pm</math> 20 min) post-dose, (6) 8 hr (<math>\pm</math> 20 min) post-dose, (7) 24 hr (<math>\pm</math> 1 hr) post-dose i.e, C1D9 pre-dose
 
C1D21 (9) Pre-dose, (10) 1 hr (<math>\pm</math> 10 min) post-dose, (11) 3 hr (<math>\pm</math> 10 min) post-dose, (12) 4 hr (<math>\pm</math> 20 min) post-dose, (13) 8 hr (<math>\pm</math> 20 min) post-dose, (14) 24 hr (<math>\pm</math> 1 hr) post-dose-i.e, C1D22 pre-dose, (15) 48 hrs (<math>\pm</math> 2hr) post-dose- i.e, C1D23 pre-dose
 
Sparse PK sampling for all participants:
 
C2D15, C3D15 trough dosing to be drawn prior to taking dose that day.
	
Pharmacodynamics (PD):	2.5 mL	Blood, Paxgene RNA tube	Phase I: C1D8 (1)Pre-dose, (2) 1 hr ( $\pm$ 10 min) post-dose, (3) 2 hr ( $\pm$ 10	Clinical Pharmacology

Test/assay	Volume (approx.)	Type of sample/tube(s) ^	Collection point	Location of specimen analysis
XPO1 mRNA expression (RT-PCR)			min) post-dose, (4) 3 hr ( $\pm$ 10 min) post-dose, (5) 4 hr ( $\pm$ 20 min) post-dose, (6) 8 hr ( $\pm$ 20 min) post-dose, (7) 24 hr ( $\pm$ 1 hr) post-dose	Program (CPP) ; [name] laboratory [name] laboratory
Next generation sequencing/ Myeloid molecular mutation panel:  TSO-500 Panel  Methylation studies per Section 5.2	2 mL per tube	Bone marrow, EDTA (lavender top) or ACD (yellow top)	(1) Baseline (2) Phase I: C1D28 (+/-3 days) (3) Phase II: C2D28 (+/-3 days) (4) Phase II:C6D28 (+/-3 days) (5) Any additional timepoints when bone marrow biopsy is done (6) Disease progression	NCI Laboratory of Pathology
Clinical MDS FISH*  *only needed if cytogenetic analysis not possible or unrevealing	3 mL per tube if bone marrow  5 mL per tube if whole blood	Blood or bone marrow aspirate, Sodium Heparin green top	(1) Baseline (2) Phase I: C1D28 (+/-3 days) (3) Phase II: C2D28 (+/-3 days) (4) Phase II:C6D28 (+/-3 days) (5) Any additional timepoints when bone marrow biopsy is done (6) Disease progression	Mayo send out test
Clinical Cytogenetics	3 mL	Bone marrow, Sodium Heparin green top	(1) Baseline (2) Phase I: C1D28 (+/-3 days) (3) Phase II: C2D28 (+/-3 days) (4) Phase II:C6D28 (+/-3 days) (5) Any additional timepoints when bone marrow biopsy is done (6) Disease progression	Mayo send out test
Additional samples (e.g., proteomics, cytokines); Section 5.2	5 mL x 2 tubes	Blood, EDTA tube	(1) Baseline (2) Phase I: C1D28 (+/-3 days) (3) Phase II: C2D28 (+/-3 days) (4) Phase II:C6D28 (+/-3 days)	CPP; [name] laboratory

Test/assay	Volume (approx.)	Type of sample/tube(s) ^	Collection point	Location of specimen analysis
			(5) Any additional timepoints when bone marrow biopsy is done (6) Disease progression	
Additional samples (e.g., proteomics, cytokines); Section 5.2	5 mL x 2 tubes	Bone marrow aspirate, EDTA tube	(1) Baseline (2) Phase I: C1D28 (+/-3 days) (3) Phase II: C2D28 (+/-3 days) (4) Phase II: C6D28 (+/-3 days) (5) Any additional timepoints when bone marrow biopsy is done (6) Disease progression	CPP; [name] laboratory
Research: Ribosome footprinting ; Quantitative mass spectrometry	10 mL	Bone marrow aspirate, EDTA tube	(1) Baseline (2) Phase I: C1D28 (+/-3 days) (3) Phase II: C2D28 (+/-3 days) (4) Phase II: C6D28 (+/-3 days) (5) Any additional timepoints when bone marrow biopsy is done (6) Disease progression	[name] laboratory

^ Tubes may be substituted based on availability with the permission of the PI or laboratory investigator.

